11.1.2 Pathological response

Extent of sampling is determined by the pre-treatment size in addition to macroscopic pathologic evaluation: at least one slide assessed by cm of tumor in the greatest diameter, i.e. 5 to 30 slides assessed, all surgically removed lymph node should be entirely submitted for histological evaluation, sectioned in two parts.

Pathological response will be assessed by microscopic histological examination on all the sections performed during the macroscopic sampling. The reporting of the 2D size of the largest distance between residual disease tumor cell nests in a cross section of the entire area of the tumor is required with relevant sections recorded on the pathology report.

In absence of tumor cells, the presence of treatment effect may provide additional information to treatment response, in comparison with lymph node pre-treatment status obtained by CT scan and mediastinal evaluation.

The cellularity is assessed across the largest cross section of residual microscopic disease as the average invasive cancer cellularity and compared and calibrated to online cellularity provided by a computer-generated standard to improve reproducibility (AACR Symmans WF) and RCB score MDAnderson.

Major Pathological Response on surgical tissue (tumor + nodes) will be defined as centrally reviewed by a panel of IFCT Pathologists, on both tumor and resected nodes, as semi-quantitative evaluation of less than 10% or remaining tumor cells, in surgical primary tumor and nodes samples (ref).

11.1.3 Evaluable for Toxicity

All patients will be evaluable for toxicity from the time of their first treatment with durvalumab.

11.1.4 Disease-free Survival

Disease-free survival shall be measured from the day of inclusion until any of the following events: day of documented equivocal or definite relapse (local, regional or distant), diagnosis of a new primary invasive cancer (except squamous cell carcinoma and basal cell carcinoma of skin and any in situ cancer, completely excised and presumed cured), or death from any cause.

NOTE: Patients with Equivocal Changes should be re-imaged at the next planned time or earlier if clinically indicated. If relapse/new primary malignancy is confirmed the date of event is taken from the date that equivocal changes were first described.

Relapse will be categorized as local/regional or distant.

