- 2 TSH may be completed within 7 days prior to visit.
- 3 Must be contrast enhanced CT scan, low dose surveillance CT is not acceptable. To ensure comparability, the baseline scans and subsequent scans to assess response must be performed using identical techniques (i.e. scans performed immediately following bolus contrast administration using a standard volume of contrast, the identical contrast agent, and preferably the same scanner).
- 4 When relapse is first documented at any site, complete restaging is required to identify all sites of relapse.

9.3 Evaluation after disease relapse or new invasive primary malignancy (during or after protocol treatment)

Should a patient relapse or develop a new invasive primary malignancy (as defined in Section 10) during the trial, details should be entered in the EDC disease event form and patient follow-up will be altered. All study patients must have a visit 4 weeks, 6 months and one year after surgery.

Treatments received by the patient after relapse and for new primary malignancies will be left to the discretion of the patient and his/her physician, but all treatments will be recorded in the EDC case report forms. All sites of NSCLC relapse or new primary malignancies will be recorded on the case report forms.

Follow up visit according to the centre practice.

Investigations		Timing
Physical Exam including:	
 • subsequent anti-cancer therapy • physical examination including pulse, blood pressure • performance status 	Every follow up visit.
Hematology	
 • CBC including hemoglobin, differential, platelet count 	Only at 4 week post surgery. Thereafter as clinically indicated only or to follow durvalumab related AEs until resolution to grade 0-1.
Biochemistry	
 • AST (SGOT) and ALT (SGPT) • alkaline phosphatase • bilirubin • creatinine 	Only at 4 week post surgery. Thereafter as clinically indicated only or to follow durvalumab related AEs until resolution to grade 0-1.
	
 • TSH¹ 	At 4 week and then as clinically indicated, or to follow durvalumab related AEs until resolution to grade 0-1. ²
	
 • INR/APTT 	As clinically indicated.
Radiology	
 • CT scan chest and upper abdomen • other imaging as clinically indicated if suspicion of relapse or new primary invasive malignancy 	According to current guidelines.

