11.1.5 Local or Regional Relapse

Local or regional relapse is defined as relapse in the area of the tumour bed, hilum or mediastinal lymph nodes.

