11.1.6 Distant Relapse

Distant relapse is defined as spread of disease beyond the area of the tumour bed, hilum or mediastinal lymph nodes.

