13 PROTOCOL TREATMENT DISCONTINUATION AND THERAPY AFTER STOPPING

13.1 Criteria for Discontinuing Protocol Treatment

Patients may stop protocol treatment in the following instances:

- Intercurrent illness which would, in the judgement of the investigator, affect assessments of clinical status to a significant degree, and require discontinuation of protocol therapy.
- Unacceptable toxicity as defined in Section 7.5 and Appendix II.
- Disease relapse or new primary invasive malignancy as defined in Section 10.
- Request by the patient.
- Pregnancy or intent to become pregnant
- Initiation of alternative anticancer therapy including another investigational agent.
- Completion of therapy as outlined in Section 7. Efforts should be made to maintain the investigations schedule and continue follow-up, even if patients discontinue protocol treatment prematurely and/or no longer attend the participating institution.

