15.3 Analysis population

- The population of tolerance is defined as all patients who received one dose of treatment

- The population the intent to treat (ITT) will include all patients included
- The population of eligible patients will consist of ITT patients presenting no deviation judged major on the criteria for inclusion and non-inclusion

The deviations to the protocol will be reviewed by the principal investigators and then classified into minor or major deviations, and listed.

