15.4 Study Endpoints and Analysis

The primary endpoint will be performed on all eligible patients based on patient percentage surgical resection R0 after a maximum of 3 cycles of chemotherapy. It will be presented associated with confidence interval of 95%.

DFS is a secondary endpoint, defined as the time from the date of inclusion to the date of first documented disease relapse or the occurrence of a new invasive primary malignancy or death from any cause. Patients who are alive and disease/new invasive primary malignancy-free at the time of each analysis will be censored at their last disease assessment date.

OS is a secondary endpoint, defined as the time from the inclusion to the date of death of any cause, or censored at their last known alive date. All analysis on DFS will be carried out for the OS endpoint.

The analysis of secondary endpoints will be performed on patient eligible.

Although PD-L1 expression as measured by immunohistochemistry is hypothesized to be a potential predictive marker, this is as yet not validated in either the adjuvant or palliative settings. Further, the cut-off defining PD-L1 positivity has not been validated. This trial will also explore the utility of PD-L1 as a predictive biomarker as well as the optimal cut-off for positivity.

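### DFS starts before surgery but gives no event or censoring date to a living patient left with unresected or gross residual tumour; separately, 13.2 contradicts 9.3 and 13.5 on follow-up after relapse

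*Protocol*

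**What the plan says.** The protocol fixes every element of DFS.

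- **Start and events.** Section 11.1.4: "Disease-free survival shall be measured from the day of inclusion until any of the following events: day of documented equivocal or definite relapse", or a new primary invasive cancer, or death. Section 15.4 repeats the start at inclusion. Under 10.1, surgery follows the infusions and is planned no later than 6 weeks after the first one, so the clock starts with the tumour in place.
- **Population.** Section 15.4: "The analysis of secondary endpoints will be performed on patient eligible". Section 15.3: "The population of eligible patients will consist of ITT patients presenting no deviation judged major on the criteria for inclusion and non-inclusion". The only surgical condition is in 10.1, which calls patients who had only a segmentectomy or wedge resection not eligible.
- **Censoring.** Section 15.4: "Patients who are alive and disease/new invasive primary malignancy-free at the time of each analysis will be censored at their last disease assessment date". There is no other DFS censoring rule.
- **Relapse.** Local or regional relapse is "relapse in the area of the tumour bed, hilum or mediastinal lymph nodes" (11.1.5). For distant relapse, 11.1.6 says: "Distant relapse is defined as spread of disease beyond the area of the tumour bed, hilum or mediastinal lymph nodes".
- **Follow-up after relapse.** Section 13.2 lists relapse or a second cancer among the reasons for withdrawal from the study. Section 9.3, which deals with relapsed patients, requires the visits at 4 weeks, 6 months and one year after surgery for all study patients. Section 13.5 follows relapsed patients until death.

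**The concern.** A DFS clock that starts before surgery needs a rule for patients who never become disease-free. The protocol foresees them: 11.1.1 defines R2 margins as tumour left behind, and Table 1 counts unoperated patients and exploratory thoracotomies. Such a patient, alive and without a recorded relapse, has no event. Not being disease-free, the patient is not covered by the censoring rule either. The analyst must choose between failure, censoring at surgery, and carrying the patient as event-free. The last two give a higher DFS.

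DFS has no target, but section 1.2 names an increase in DFS as part of the expected benefit and plans to correlate response and immune findings with it. The unclassified patients are those in whom neoadjuvant treatment followed by surgery did not achieve its aim.

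The conflict over 13.2 concerns OS. If a site stops following a patient at relapse, the later death is not recorded and the patient is censored at the last date known alive, which flatters OS.

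**Working it through.** **The plan's own figures.** The protocol gives no DFS rate, event count or power, so there is no DFS figure to reproduce. The primary design does reproduce: with the two-stage rule of 15.2 (stop at 34 or fewer of 39; success at 71 or more of 77), exact binomial sums give a one-sided type I error of 0.042 at 85% and power of 0.895 at 95%. Nothing below changes that.

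**Which patients are unclassified.** Reading 11.1.4, 11.1.5, 11.1.6 and 15.4 together:

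- Death, new primary or distant spread: an event, before or after surgery.
- Alive, completely resected, no relapse: censored.
- Alive, R1 with clear imaging, possibly after the adjuvant therapy allowed by 13.4: may be judged disease-free and censored.
- Locoregional progression before surgery: ambiguous. The heading of 9.3 reads "Evaluation after disease relapse or new invasive primary malignancy (during or after protocol treatment", and 13.1 lists "Disease relapse or new primary invasive malignancy as defined in Section 10" as a reason to stop treatment, so relapse before surgery is contemplated. Section 11.1.5, however, defines local or regional relapse only as relapse in the named sites.
- Alive, unresected or macroscopically residual local tumour, never called relapse: no event and no censoring date.

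**How many.** Inputs from Table 1, the 528-patient reference trial: 509 operated, 4 exploratory thoracotomies, 484 complete resections.

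- Clearly unresected: (528 − 509) + 4 = 19 + 4 = 23; 23/528 = 4.4%; 0.0436 × 77 = 3.4, about 3 patients.
- Upper bound, all without complete resection: 528 − 484 = 44; 44/528 = 8.3%; 0.0833 × 77 = 6.4, about 6 patients.
- A trial that meets its success rule has at most 77 − 71 = 6 non-R0 patients; 6/77 = 7.8%.

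**Effect on 12-month DFS.** Let f be the fraction of such patients, s the DFS in the rest, and u the share of such patients with no other DFS event by 12 months. Assumptions, not protocol values: s = 85%, u = 50% to 80%.

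- Counted as failures: (1 − f)s.
- Carried as event-free until another event: (1 − f)s + fu, a rise of fu.
- Censored at surgery: about s, a rise of fs.

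| f | rise if carried as event-free (fu) | rise if censored at surgery (fs) |
|---|---|---|
| 4.4% | 2.2 to 3.5 points | 3.7 points |
| 7.8% (upper bound) | 3.9 to 6.2 points | 6.6 points |
| 8.3% (upper bound) | 4.2 to 6.7 points | 7.1 points |

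For scale, the standard error of an 85% proportion with n = 77 is √(0.85 × 0.15/77) = 4.1 points.

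**Follow-up after relapse.** No arithmetic applies. Section 13.2 ends study participation at the event after which 13.5 requires follow-up until death. The pointers in 13.5 do not resolve this: 8.2 is premedication, 8.3 is infusion monitoring and 10 is surgery and pathology. The matching texts are 9.2, 9.3 and 11.

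**The case against.** The other side has a good deal of ground.

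- **The gap is narrow.** Radiological change suffices for a suspicious local relapse (11.2.1), equivocal relapse counts (11.1.4), and 11.3 allows dating in retrospect. A growing unresected tumour might well be recorded as relapse. This stands as an ambiguity, but it does not reach tumour that stays in place without progressing.
- **It may be SAP detail.** Derivation rules for a few patients often go there, and the SAP is not shown. But the protocol itself fixes start, events, population and censoring, and together they leave a foreseeable group out.
- **The larger figures are too high.** A reader might infer that every non-R0 patient is unclassified. The documents do not support that. An R1 patient with clear imaging may count as disease-free. Section 1.2 also makes nodal dissection and a negative highest mediastinal node part of complete resection, and if Table 1 used a similar definition (not stated), some of its 21 incomplete resections need not have had residual tumour. Even the 4.4% is imperfect: no reasons are given for the 19 not operated, and any who died or developed metastases would already be events. It also leaves out any R2 cases among the 21.
- **Counting every non-resection as an event is a choice of estimand.** Refusal and toxicity differ from progression. This stands and shapes the fix.
- **On 13.2,** the more specific texts keep follow-up, and 13.1 asks for follow-up to continue after early stopping of treatment. A reader might infer that OS will be overstated. That holds only to the extent that sites act on 13.2, which cannot be quantified from the protocol.

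**Conclusion.** The point holds in a limited form. DFS has no rule for a living patient with unresected or macroscopically residual local tumour that is never called relapse. At the reference trial's 4.4% this concerns about 3 of 77 patients and moves 12-month DFS by roughly 2 to 4 points, less than one standard error. That rests on the reference rate applying here, on 50% to 80% of these patients having no other event by 12 months, and on 85% DFS in the rest. The 7.8% to 8.3% rows are upper bounds only.

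The contradiction between 13.2 and 9.3/13.5 is plain on the text and is the firmer part; its effect on OS depends on site behaviour. Only secondary endpoints are touched. The primary R0 analysis and the sample size stand. Both parts should be corrected because the direction of error is favourable and the repair is cheap.

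**What to change.** 1. Reconcile 13.2 with 9.3 and 13.5 so that relapse or second cancer does not end survival follow-up. Correct all three stale pointers in 13.5 (8.2, 8.3 and 10).
2. In 11.1.4 and 15.4, count progression precluding surgery and macroscopic residual disease (R2 or exploratory thoracotomy) as events, dated at surgery or at the decision not to operate. State how R1 with clear imaging and non-resection for other reasons (refusal, toxicity) are handled. Add a sensitivity analysis that counts all non-resections as events.
3. Fix the rule before the DFS analysis and document that it was set without reference to outcome data. The trial is unblinded (15.1), and 15.5 implies that at least 45 patients were enrolled before it resumed, so a late change could look data-driven.

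Cost: amendment wording in four sections. Completeness of resection must already be described (10.1). The protocol does not mention recording the date of a decision not to operate, so it would have to be retrieved for the few unresected patients already enrolled (about 0.0436 × 45 = 2 at the reference rate). DFS will come out slightly less favourable.

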11.1.5 Local or Regional Relapse

Local or regional relapse is defined as relapse in the area of the tumour bed, hilum or mediastinal lymph nodes.

11.1.6 Distant Relapse

Distant relapse is defined as spread of disease beyond the area of the tumour bed, hilum or mediastinal lymph nodes.

11.1.7 Overall Survival

Overall survival is defined as the time from inclusion to the time of death (from any cause) or to the date the patient was last known to be alive.

11.2 Evidence of Disease Relapse

When relapse is first documented at any site, complete restaging is required to identify all sites of relapse.

11.2.1 Local or Regional Relapse

1. Definite - positive cytology, aspiration, or biopsy
2. Suspicious - radiological changes suggesting relapse

11.2.2 Distant Relapse

This is documented only when definite evidence is available but may be dated retrospectively to first onset of a suspicious sign as defined below.

1. Definite (one of 1a or 1b)
 - a) Biopsy or cytology proven disease.
 - b) New lesions present on clinical examination, ultrasound, CT, or MRI scan that are strongly suggestive of metastatic cancer, that cannot be attributed to other disease, and that cannot reasonably be confirmed by biopsy or cytology. PET imaging can be used to confirm findings from other imaging modalities.
2. Suspicious

- a) New lesions present on clinical examination, ultrasound, CT, or MRI scan that are suggestive of metastatic cancer, that are unlikely to be attributable to other disease, and that cannot reasonably be confirmed by biopsy or cytology.

11.3 Dating of First Relapse

This should always be based on the first onset of a sign but never on the onset of a symptom. The date of first detection of a palpable lesion is acceptable only when the diagnosis of tumour involvement is subsequently established. The diagnosis of recurrent disease by radiographs or scans should be dated from the date of the first positive record, even if this is determined in retrospect

11.4 Management Following Relapse

Patient management following local, regional or distant relapse is at the discretion of the investigator.

11.5 New Primary Malignancy

Should be pathologically confirmed and recorded in the case report forms.

Patient management following new primary malignancy is at the discretion of the investigator, but all treatments need to be documented.

12 SERIOUS ADVERSE EVENT REPORTING

12.1 Definition of Serious Adverse Event

A serious adverse event is one that at any dose (including overdose):

- Results in death.
- Is life-threatening.¹
- Requires inpatient hospitalization or prolongation of existing hospitalization².
- Results in persistent or significant disability or incapacity.³
- Is a congenital anomaly or birth defect.
- Is an important medical event.⁴

1 “Life-threatening” means that the subject was at immediate risk of death at the time of the serious adverse event; it does not refer to a serious adverse event that hypothetically might have caused death if it were more severe.

2 The following hospitalizations are not considered SAEs:

- Hospitalization < 24h
- Planned hospitalization required by the protocol (e.g., for study drug administration or to perform an efficacy measurement for the study)
- Hospitalization for a preexisting condition, provided that all of the following criteria are met:
 - The hospitalization was planned prior to the study or was scheduled during the study when elective surgery became necessary because of the expected normal progression of the disease.
 - The patient has not experienced an adverse event.
 - Routine health assessment requiring admission for baseline/trending of health status (eg, routine colonoscopy)
 - Admission encountered for another life circumstance that carries no bearing on health status and requires no medical/surgical intervention (eg, lack of housing, economic inadequacy, caregiver respite, family circumstances, administrative reason).

3 “Persistent or significant disability or incapacity” means that there is a substantial disruption of a person’s ability to carry out normal life functions.

4 Medical and scientific judgment should be exercised in deciding whether expedited reporting is appropriate in situations where none of the outcomes listed above occurred.

12.1.1 Definition of adverse events of special interest (AESI)

An adverse event of special interest (AESI) is one of scientific and medical interest specific to understanding of the Investigational Product and may require close monitoring and rapid communication by the

investigator to the sponsor. An AESI may be serious or non-serious. The rapid reporting of AESIs allows ongoing surveillance of these events in order to characterize and understand them in association with the use of this investigational product.

AESIs for durvalumab include but are not limited to events with a potential inflammatory or immune-mediated mechanism and which may require more frequent monitoring and/or interventions such as steroids, immunosuppressants and/or hormone replacement therapy. These AESIs are being closely monitored in clinical studies with durvalumab monotherapy and combination therapy. An immune-related adverse event (irAE) is defined as an adverse event that is associated with drug exposure and is consistent with an immune-mediated mechanism of action and where there is no clear alternate aetiology. Serologic, immunologic, and histologic (biopsy) data, as appropriate, should be used to support an irAE diagnosis. Appropriate efforts should be made to rule out neoplastic, infectious, metabolic, toxin, or other etiologic causes of the irAE.

If the Investigator has any questions in regards to an adverse event (AE) being an irAE, the Investigator should promptly contact IFCT.

AESIs observed with durvalumab include:

- Colitis
- Pneumonitis
- ALT/AST increases / hepatitis / hepatotoxicity
- Neuropathy / neuromuscular toxicity (i.e. events of encephalitis, peripheral motor and sensory neuropathies, Guillain-Barré, and myasthenia gravis)
- Endocrinopathy (i.e. events of hypophysitis, adrenal insufficiency, and hyper- and hypothyroidism)
- Dermatitis
- Nephritis
- Pancreatitis (or labs suggestive of pancreatitis - increased serum lipase, increased serum amylase)

Further information on these risks (e.g. presenting symptoms) can be found in the current version of the durvalumab Investigator Brochure.

Important medical events that may not be immediately life-threatening or result in death or hospitalization but may jeopardize the patient or may require intervention to prevent one of the other outcomes listed in the definition above should also usually be considered serious. Examples of such events include allergic bronchospasm requiring intensive treatment in an emergency room or at home, blood dyscrasias or convulsions that do not result in inpatient hospitalization, or the development of drug dependency or drug abuse.

A diagnosis of cancer during the course of a treatment should be considered as medically important. The List of Critical Terms (1998 adaptation of World Health Organization Adverse Reaction Terminology Critical Terms List, provided in the “Instructions for completing the ‘Serious Adverse Event/Expedited Report from a Clinical Trial’ form”) should be used as guidance for adverse events that may be considered serious because they are medically important.

Clarification of the difference in meaning between “severe” and “serious”

The term “severe” is often used to describe the intensity (severity) of a specific event (as in mild, moderate, or severe myocardial infarction); the event itself, however, may be of relatively minor medical

significance (such as severe headache). This is not the same as “serious”, which is based on the outcome or action criteria usually associated with events that pose a threat to life or functioning. Seriousness (not severity) serves as a guide for defining regulatory reporting obligations.

SAEs/AEs will be reported up to one month after surgery, and SAEs notification will be made within 24 hours.

